Isosorbide Mononitrate For Anti-Vascular Endothelial Growth Factor (VEGF) Induced Kidney Injury

NCT04051957

Version Date: 10/24/2019

1 Isosorbide Mononitrate For Anti-Vascular Endothelial Growth Factor (VEGF) Induced Kidney
2 Injury

3
4 **SPECIFIC AIM:**

5 To test the hypothesis that isosorbide mononitrate prevents deterioration of renal function in patients
6 receiving anti-angiogenic therapies that target vascular endothelial growth factor (VEGF).
7
8
9
10
11
12
13
14
15
16
17
18
19
20
21
22
23
24
25
26
27
28
29
30
31
32
33
34
35
36
37
38
39
40
41
42
43
44
45
46
47
48
49

BACKGROUND AND SIGNIFICANCE: Anti-angiogenic drugs that target VEGF (bevacizumab) and its receptors (sunitinib, sorafenib, pazopanib, and axitinib) are part of standard treatment for patients with renal cell carcinoma, non-small cell lung carcinoma, colorectal carcinoma, and gastrointestinal stromal tumors¹. However, because of their action on VEGF expression levels, the use of these medications has been associated with significant kidney damage and hypertension. Indeed, the use of anti-angiogenic therapies is frequently halted in cancer patients because of worsening kidney function, hypertension, and proteinuria with the subsequent delay, interruption or reduction of effective dose in patients requiring this treatment modality¹.

Importantly, many of the kidney-related side effects of antiangiogenic and anti-VEGF therapies have been attributed to the downregulation of nitric oxide (NO) bioavailability¹. In support of a modulatory effect of VEGF on NO, it has been shown that VEGF infusion results in a significant drop in blood pressure mainly through stimulation of eNOS (endothelial NO synthase) and consequent NO release^{2,3}. NO activation and enhanced synthesis lead to vasodilation in the renal microvasculature, which results in lowering of blood pressure and other modulatory effects on kidney function.

PRELIMINARY STUDIES: Cancer patients receiving anti-VEGF therapy share similar pathophysiological renal changes as seen in women with preeclampsia^{8,9}. Endothelial dysfunction in preeclampsia results from reduction in NO bioavailability⁴. Interestingly, eNOS uses nitrates as a substrate, and hence several studies have examined the utility of using organic nitrates as a possible treatment for NO deficiencies in preeclampsia. Although these studies were not powered to identify alterations in maternal and fetal outcomes, they did highlight the potential use of organic nitrates as antihypertensive agents in pre-eclampsia^{5,6,7}. Moreover, recent studies have shown that NO donors normalize blood pressure in anti-VEGF induced hypertension¹⁰. The same authors went on to devise a treatment algorithm distinguishing three groups of patients on anti-VEGF treatment: normotensive (<120/<80 mm Hg); prehypertensive (120-130/80-89 mm Hg) and hypertensive (>140/>90 mm Hg). They suggested no pharmacological treatment for normotensive patients, starting NO donors only for those pre-hypertensives with evidence of organ damage, and starting with NO donors as antihypertensive agents for the hypertensives along with weekly blood pressure checks¹¹. In their paper, they suggest that pre-treatment with long lasting NO donors may protect against the development of VEGF pathway inhibitor (VPI)- induced hypertension. They suggest the start of treatment 7-10 days before the initiation of VPI therapy. The paucity of large clinical studies in the literature using NO donors to protect against the development of proteinuria and hypertension and cancer patients receiving VPI therapy prompted us to investigate this modality of treatment.

RATIONALE OF DOSE: Preliminary data from a trial done to study single dose effects of isosorbide mononitrate (IMN) alone or in combination with losartan on central blood pressure showed that the mean placebo-subtracted decrease from baseline in augmentation index was highest in those patients who received 60 mg IMN with or without losartan¹². An effectiveness of extended release nitrate study for treatment of systolic hypertension used 60 mg and 120 mg strength tablets and showed statistically significant changes in the augmentation index and decreasing pulse pressure¹³. No studies have checked the effect on proteinuria. Accordingly, 60 mg and 120 mg of IMN will be used in the present study

SAFETY OF ISOSORBIDE MONONITRATE: The FDA indication for IMN is for prevention of angina pectoris (<https://druginserts.com/lib/rx/meds/imdur/>). Per the package insert as referenced in link, there is no evidence of carcinogenicity, gene mutation or chromosome aberrations at biologically relevant concentrations. Side effects include nausea, dizziness, headache, symptomatic hypotension

1
2
3
4
5
6
7
8
9
10
11
12
13
14
15
16
17
18
19
20
21
22
23
24
25
26
27
28
29
30
31
32
33
34
35
36
37
38
39
40
41
42
43
44
45
46

MATERIAL AND METHODS:

Study Population: Adult patients who are referred to the Adult Nephrology Clinic at The University of Texas Health Science Center at Houston for evaluation and treatment of acute kidney injury, hypertension and/or proteinuria while either on or enrolled with anti-VEGF therapies, will be included in the study. The protocol is currently being submitted to the University of Texas Health Science Center at Houston IRB. Informed consent in the native language of each patient will be obtained prior to enrollment.

Inclusion Criteria: Patients on or enrolled for anti-VEGF therapy and having new-onset proteinuria, defined as a urine protein: creatinine ratio (UPC) of >500mg/g or hypertension (Systolic BP \geq 140 mm Hg and/or diastolic BP \geq 90 mm Hg) or a decrease in eGFR by \geq 25% from baseline before starting therapy.

Exclusion Criteria: Pregnant women and breast-feeding women. Patients >65 years will be excluded.

Protocol and Treatment Plan: The patients will have baseline blood pressure (BP), UPC, weight, serum basic metabolic panel and eGFR measured prior to being assigned into groups. All current prescribed and over the counter medications will be documented. Patients will be allocated to the treatment or placebo arms by simple randomization. BP will be measured in the right arm of patients, in the seated position, using arm cuff and automated office blood pressure by oscillometry method. Three measurements will be taken one minute apart, and the average of each of the systolic and diastolic measurements will be charted as the blood pressure recording for the visit. Pregnancy and breast feeding status will be established by self-reporting by female patients.

Patients in the treatment arm will be started on IMN 60 mg ER daily. The dose of IMN will be escalated to 120 mg ER (two tablets of 60 mg ER) after 4 weeks of start of therapy, if no response as per our response criteria (as below) is achieved. The grace period for follow up appointments would be +/- 3days to account for clinic closure, weather changes or patient's inability to come to clinic due to non-medical reasons.

The drug and placebo will be compounded in Compounding Shop Pharmacy, [name]. Even though we will be using the drug for a non-FDA approved use of IMN, we will not be needing IND for the study drug due to the low risk profile of the drug. Drug accountability by IDS will include for storage, labeling, dispensing and disposal of the study drug and placebo.

Criteria for Response (one or more of the following)

1. Improved eGFR \geq 25% from prior to enrollment.
2. Reduction in proteinuria of \geq 25% from prior to enrollment.
3. Reduction in SBP of \geq 10 mm Hg and/or DBP \geq 5 mm Hg from prior to enrollment

Study design:

The patients will be allocated by simple randomized into the two groups (20 patients per group). The study will be double-blinded

Group 1: (Treatment group). The starting dose will be Imdur 60 mg ER daily and after 4 weeks, if tolerated but response is not achieved, the dose will be escalated to Imdur 120 mg ER daily (2 tabs of 60 mg ER tablets). This would be done in addition to the standard of care treatment with either angiotensin converting enzyme inhibitor (ACEI) or calcium channel blockers to treat hypertension as needed.

Group 2: (Placebo group): Placebo will be given along with the standard of care treatment with either ACE I or calcium channel blockers to treat hypertension as needed. The tablets of placebo will be doubled after 4 weeks of start of therapy. This will help eliminate bias in this double-blinded study.

1
2 **Follow-up:** Systolic BP will be monitored on a weekly basis for three months. The patients will
3 record their BPs at home with their automated machines and will either call in with the results or bring
4 their records during the next clinic visit. The eGFR and serum creatinine (included in the basic
5 metabolic panel) will be measured as per protocol laboratory workup done within 15 days of
6 enrollment. This will be done once a month during clinic visits. The grace period for follow up
7 appointments would be +/- 3 days to account for clinic closure, weather changes or patient's inability to
8 come to clinic due to non-medical reasons. A follow up phone call will be done every month (weeks 6,
9 10, 14 and 17 weeks) for 3 months. Antihypertensive medications that the patients have been taking
10 prior to enrollment will be continued. Any reduction in the need for antihypertensive medications will
11 be documented. UPC will be measured at the time of enrollment and then monthly.

12
13 **Primary End Points:**

- 14
- Reduction in UPC of $\geq 25\%$ from that measured before enrollment

15 **Secondary End Points:**

- 16
- Improved eGFR $\geq 25\%$ from before enrollment.
 - Reduction in SBP of ≥ 10 mm Hg and/or DBP ≥ 5 mm Hg from before enrollment
- 17
18

19 Both the primary and secondary outcomes will be measured for every month for the 3 months that the
20 patient is in the trial. All patients will continue treatment for the entire 3 months to help with data analysis
21 for future larger randomized controlled studies. The grace period for follow up appointments would be
22 +/- 3days to account for clinic closure, weather changes or patient's inability to come to clinic due to
23 non-medical reasons.

24 **MONITORING/ EVALUATION DURING STUDY:**

25 Baseline BP, serum creatinine, eGFR, and UPC will be recorded at the time of enrollment. For blood
26 testing 2cc of serum will be collected and for urine testing 2 ml of urine will be
27 collected, and sent to the Memorial Herman outpatient laboratory. Blood pressure will
28 be monitored on a weekly basis starting from the time of enrollment. In those who are already on BP
29 medications, BPs will be recorded on a weekly basis, and any need for reduction/increase in the
30 doses/addition of new medications will be document. Patients will be given a log book
31 to record their BPs. Patients will be monitored for 3 months. UPC and serum creatinine will
32 be measured on a monthly basis.

33 If side effects (nausea, dizziness, headache, symptomatic hypotension) are observed to the increased
34 dose of 120 mg/day, the dose will be reduced back to the 60 mg d.

35 **Confidentiality Plan:**

36 All data obtained, including concomitant medications will be entered in Red Cap. All serious adverse
37 events will be forwarded to FDA according to the UT Health Science Center at Houston institutional
38 policy. All records will be maintained at UT Heath Science center. The Data Safety Monitoring board
39 will be involved in safety monitoring.

40 **Possible Side Effects:**

41 Minor side effects of Imdur have been noted, including headache, dizziness, hypotension and nausea.
42 As per FDA approved package insert, headache and dizziness was reported in $>5\%$ of the patients. These
43 symptoms are dose dependent and tend to disappear with continued use.

1 Criteria for Removal:

2 With the increased dose of Imdur, if side effects such as symptomatic hypotension, nausea, headache
3 or dizziness the dose will be reduced to 60 mg ER. If it is the starting dose (60 mg ER) which caused
4 these effects, then the patient will be taken off the drug, and will be observed for Intension to Treat
5 (ITT) analysis. The Severe Adverse Effect (SAE) will be reported according to the UT Health Science
6 Center at Houston institutional policy. Criteria for removal would be uncontrolled nausea, headache,
7 symptomatic hypotension or dizziness. We will also monitor for any worsening of renal function or
8 proteinuria.

9 Limitations:

10 This is a pilot study and therefore it is may not be powered to detect difference with treatment. The small
11 sample size may not allow the data to be statistically significant. It is unclear if other antihypertensive
12 medications will confound the results. Once preliminary data is available, the study population will be
13 increased for a larger clinical trial.

14

15 Expected results:

16 There will be statistically significant response seen with therapy in the patients. The study is a pilot study
17 and will help in establishing the basis of a larger randomized controlled study.

REFERENCES:

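### The aim is to prevent loss of renal function, but every named endpoint counts improvement only, and the one eGFR endpoint can hardly detect prevention

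*Protocol*

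**What the plan says.** - **Aim.** The Specific Aim, the only one, is "To test the hypothesis that isosorbide mononitrate prevents deterioration of renal function in patients" receiving anti-VEGF therapy.
- **Population.** Study Population takes patients referred "for evaluation and treatment of acute kidney injury, hypertension and/or proteinuria while either on or enrolled with anti-VEGF therapies". Under Inclusion Criteria any one of three findings is enough: new-onset proteinuria, hypertension, "or a decrease in eGFR by" at least 25% from the value before therapy.
- **Endpoints.** The primary is "Reduction in UPC of" at least 25%. The secondaries are "Improved eGFR" by at least 25%, and a fall of at least 10 mm Hg systolic and/or 5 mm Hg diastolic. The Criteria for Response list the same three improvements.
- **Worsening.** Worsening of renal function or proteinuria appears only under Criteria for Removal, as something to be monitored. It has no threshold, no comparison between arms and no endpoint status.
- **Data.** Protocol and Treatment Plan has "eGFR measured prior to being assigned into groups". For eGFR and creatinine, Follow-up says "This will be done once a month during clinic visits". The endpoint section adds "Both the primary and secondary outcomes will be measured for every month for the 3 months that the" patient is in the trial.
- **Size and purpose.** There are 20 patients per group. Limitations and Expected results describe a pilot that is to prepare a larger randomised trial.

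**The concern.** A preventive effect means that eGFR stays level on IMN while it falls on placebo. An endpoint that counts only gains of 25% or more gives both patients the same score, zero. So no named endpoint measures the hypothesis as worded, and the one that uses eGFR discards nearly all the information about it.

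The entry criteria add to this. A patient who enters on proteinuria or blood pressure may have lost little or no eGFR and so has little to regain. The referral population, with injury already present, suits an aim of treatment better than one of prevention.

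The eGFR data will exist whatever the endpoint, so a mean change could be computed afterwards. What is at stake is that the named endpoints of a pilot meant to prepare a larger trial do not define that estimate.

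**Working it through.** The protocol states no alpha, effect size, SD or event rate, so there is no calculation of its own to reproduce. What follows is an illustration.

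**Inputs.** From the protocol: 20 per arm, a 25% eGFR gain threshold, 3 months. Assumed: two-sided alpha 0.05; percent change in eGFR normal with equal SD in both arms; IMN mean 0; placebo mean −10 or −15; SD 15 or 20 points.

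**Step 1: responder rates.** P(gain ≥25%) is 1 − Φ(25/SD) on IMN and 1 − Φ((25 + fall)/SD) on placebo.
- SD 15: IMN 4.8%; placebo 1.0% (fall 10) or 0.4% (fall 15). Expected improvers of 20: 0.96 against 0.20 or 0.08.
- SD 20: IMN 10.6%; placebo 4.0% or 2.3%. Expected improvers of 20: 2.1 against 0.8 or 0.5.

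**Step 2: what Fisher's exact test needs.** 4 v 0 of 20 gives p = 0.106; 5 v 0 gives p = 0.047. So IMN needs at least 5 improvers even if placebo has none, where about 1 or 2 are expected.

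**Step 3: power.** The binary endpoints use exact enumeration of all 21 × 21 outcomes. Mean change uses the noncentral t with 38 df and noncentrality fall/(SD·√(2/20)). For example, 10/(15 × 0.316) = 2.11.

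| Placebo fall, SD | Gain ≥25% | Decline ≥25% | Mean change |
|---|---|---|---|
| 10%, SD 15 | 0.2% | 8.7% | 54% |
| 15%, SD 15 | 0.2% | 31.6% | 87% |
| 10%, SD 20 | 2.5% | 9.8% | 34% |
| 15%, SD 20 | 3.4% | 24.3% | 64% |

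The decline column uses Φ(−25/SD) on IMN against Φ((−25 + fall)/SD) on placebo. At SD 15 that is 4.8% against 15.9% or 25.2%. Reversing the threshold helps, but it remains weak for falls of this size.

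The low figures for the gain endpoint come partly from Fisher's test being conservative when events are rare. The normal approximation gives 11% to 18% in the same four cells, which is still low.

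**Step 4: wider range.** Over SD 10 to 25 and placebo falls of 10% to 25%, Fisher power for the gain endpoint is at most 13.6% (SD 25, fall 25%). Mean change has more power in every cell, 23% or more.

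**Step 5: what the gain endpoint can detect.** For 80% Fisher power, the mean gain on IMN would have to be, with placebo at −10 / −15:
- SD 12: 19.3 / 19.2 points
- SD 15: 18.8 / 18.1 points
- SD 20: 20.8 / 18.6 points

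A mean rise of about 18% to 21% is improvement, not prevention.

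**Step 6: who can score by recovery.** A 25% gain that does not exceed the pre-therapy eGFR needs an earlier loss of at least 1 − 1/1.25 = 20%. Patients with a smaller loss cannot reach it by recovery. A patient who enters with exactly a 25% loss must reach 0.75 × 1.25 = 0.9375 of the pre-therapy value, which is (0.9375 − 0.75)/0.25 = 75% of the loss regained.

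**The case against.** **The eGFR endpoint is only one of two secondaries.** The primary is UPC, and a preventive effect can show there. If placebo UPC doubles while IMN holds it, with a log-scale SD of 0.4 to 0.7, Fisher power is 41% to 53%; if placebo UPC rises 25%, it is 7% to 12%. This stands: the power argument is confined to eGFR.

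**Renal function may be meant broadly.** The preliminary-studies section speaks of protecting against proteinuria and hypertension, which two of the three endpoints measure. That softens the charge. But the background lists worsening kidney function separately from those two, and their endpoints also count only improvement.

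**The numbers are assumed, and a wider spread narrows the contrast.** At SD 30, power for gain against mean change is 5% v 18% with a 10% placebo fall, and 9% v 34% with a 15% fall. With a 25% fall the gain endpoint reaches 18%. If IMN averages +10% or +15% with placebo 15 points lower at SD 15, the gain endpoint has 14% or 32%. So the exact ratio is uncertain, but the direction is not: mean change has more power in every preventive scenario examined. The last two cases include a mean gain on IMN, so they are not purely preventive. Normality in a mixed population that includes acute kidney injury is also only an approximation. How many patients lie below the 20% loss in step 6 is unknown.

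**It is a pilot, and the analysis plan is not shown.** The Limitations excuse low power and possible confounding by other antihypertensives. They do not address endpoints that point away from the aim. The aim and the endpoints are both fixed in the protocol itself, so the mismatch is not a detail left to the analysis plan.

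**Conclusion.** The concern holds. That the aim is prevention while all named endpoints count improvement follows from the text alone and needs no assumption.

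That a purely preventive effect is almost undetectable on the eGFR endpoint rests on the assumed spread and placebo decline: at most 13.6% power over SD 10 to 25 and falls of 10% to 25%, and at most 18% when SD 30 is included. It does not extend to UPC or blood pressure. The trial can run as written and the eGFR data will not be lost, so this is a change that should be made rather than a bar to starting.

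**What to change.** The sponsor should decide which question the trial asks, then make one of two changes.

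1. **If prevention is meant:** make the secondary kidney-function endpoint the change in eGFR from the pre-randomisation value to month 3, compared between arms with adjustment for baseline eGFR. Report the proportions with at least 25% decline and at least 25% improvement descriptively. The primary UPC and the blood pressure endpoints stay as they are, so the aim is then answered at the secondary level. The Criteria for Response, which the protocol uses for dose escalation, are not part of this proposal.
2. **If treatment of established injury is meant,** as the Study Population suggests: restate the aim as improvement of established anti-VEGF kidney injury, so that it matches the endpoints.

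The first costs one endpoint definition and one regression on eGFR values already collected before allocation and monthly in both arms. The second costs one sentence. Neither needs extra visits, samples or patients.

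### The sole primary endpoint is a relative UPC fall, but patients may enter at any UPC and simple randomisation leaves both baseline UPC and the 20 per group to chance; stratified blocks and a baseline-stratified analysis would be a cheap improvement.

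*Protocol*

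**What the plan says.** **Entry.** The Inclusion Criteria require a patient "having new-onset proteinuria, defined as a urine protein: creatinine ratio (UPC) of >500mg/g or hypertension", or an eGFR fall of at least 25%. The routes are alternatives, and only the first carries a UPC threshold.

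**Endpoint.** Primary End Points lists one item: a UPC reduction of at least 25% "from that measured before enrollment". No minimum baseline UPC is set.

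**Allocation.** Protocol and Treatment Plan: "Patients will be allocated to the treatment or placebo arms by simple randomization". Study design repeats that patients are "allocated by simple randomized into the two groups (20 patients per group"). No stratification factor is named. Baseline values are available in time to serve as one: "UPC, weight, serum basic metabolic panel and eGFR measured prior to being assigned into groups".

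**Purpose.** Limitations says that the trial is a pilot and "therefore it is may not be powered to detect difference with treatment". Expected results says that it "will help in establishing the basis of a larger randomized controlled study". On prior evidence, Rationale of Dose says: "No studies have checked the effect on proteinuria".

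**The concern.** Entry rule and endpoint do not match. A patient who enters through hypertension or eGFR decline may have any UPC, yet is scored on a relative UPC fall. A fall that lies wholly below the protocol's own 500 mg/g threshold counts the same as one in a patient with marked proteinuria. The pooled responder rate is then a weighted average over a mix that nothing in the protocol controls.

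Baseline UPC also predicts this endpoint when the drug does nothing. Spot values vary, so some falls of 25% or more are chance. Patients selected for a high first value show more of them, through regression to the mean. Simple randomisation leaves the split of such patients between arms to luck, and does not secure the stated group size.

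At stake is mainly what the pilot can hand on to the larger trial. A pooled rate on its own cannot say whether UPC fell in proteinuric patients or elsewhere.

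**Working it through.** **Inputs from the protocol:** 20 per group, 40 in total; simple randomisation; threshold 500 mg/g; response = UPC fall of at least 25%. The protocol gives no derivation of the 20, so there is no figure to reproduce.

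**Assumptions (not in the protocol):** share above 500 mg/g 50% unless stated; within-person SD of log UPC 0.35 (range 0.25 to 0.50); median UPC 300 to 500 mg/g; between-person log SD b from 0.6 to 1.0; one follow-up value; the same baseline value used for stratum and endpoint.

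**1. No floor.** 60/80 = 0.75, so 80 to 60 mg/g is a 25% fall and a primary success.

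**2. Group size.** For 40 coin tosses, P(exactly 20 and 20) = C(40,20)/2^40 = 0.125.

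**3. Imbalance in patients above 500 mg/g (20 of 40).**

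| Arms differ by | Arms held at 20/20 (hypergeometric) | Coin toss (Binomial(20, 0.5)) |
|---|---|---|
| 4 or more | 0.343 | 0.503 |
| 6 or more | 0.113 | 0.263 |

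**4. Chance response without a drug effect.** Let B be baseline log UPC with variance b² + SD², and D the change with variance 2·SD², so cov(B, D) = −SD². The unselected rate is Phi(ln 0.75/(SD·√2)), which is 0.281 at SD 0.35. Conditioning on B above or below ln 500:

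| SD | Above 500 | Below 500 | Gap |
|---|---|---|---|
| 0.25 | 0.247–0.323 | 0.145–0.182 | 0.079–0.147 |
| 0.35 | 0.344–0.453 | 0.183–0.238 | 0.126–0.224 |
| 0.50 | 0.436–0.569 | 0.205–0.278 | 0.188–0.305 |

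**5. Effect of imbalance.** Shift in the expected rate difference = (imbalance/20) × gap. At SD 0.35, an imbalance of 4 gives 0.2 × 0.126 to 0.2 × 0.224, or 2.5 to 4.5 points; an imbalance of 6 gives 3.8 to 6.7. The standard error of the difference at a 28% rate is √(2 × 0.28 × 0.72/20) = 14.2 points.

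**6. Dependence on mix.** With share f above 500 mg/g, pooled difference = f × (effect above) + (1 − f) × (effect below). If a 40-point effect were confined to patients above 500 mg/g, the pooled difference would be 40, 30, 20 or 10 points at f = 100%, 75%, 50% or 25%. Stratified allocation does not change f. In simulation at f = 50% (20% versus 60% above, 20% in both arms below), power is 0.28 under simple and under stratified allocation.

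**7. What stratified allocation buys.** Take median 500 and b = 0.8. Above: 0.357 placebo versus 0.756 (a 40% true fall). Below: 0.204 placebo versus 0.204, 0.357 or 0.592 (true fall 0, 20% or 40%).

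| Quantity | Stratified blocks | Simple |
|---|---|---|
| SD of crude difference, no effect below | 0.136 | 0.149 (coin toss) |
| SD, 20% fall below | 0.142 | 0.151 (coin toss) |
| SD, 40% fall below | 0.143 | 0.147 (coin toss) |
| Power of stratified exact test (three cases) | 0.18 / 0.34 / 0.61 | about 0.21 / 0.37 / 0.64 |
| Mean 95% half-width above 500 mg/g | 39.9 points | 40.4 (20/20) to 41.0 (coin toss) |

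The first stratified SD checks by hand: √[(10/400) × (0.756×0.244 + 0.204×0.796 + 0.357×0.643 + 0.204×0.796)] = 0.136. The reduction in SD is about 3% to 9%. The half-width is 1.96 × √(0.357×0.643/10 + 0.756×0.244/10) = 0.399.

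**8. What stratifying the analysis buys.** In the same three cases, a pooled Fisher test has power 0.15, 0.30 and 0.58, against 0.18, 0.34 and 0.61 for the stratified exact test (10 per arm per stratum).

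**The case against.** The strongest reply is that stratified allocation does not touch the main defect. It balances the mix between arms but leaves the overall mix and the missing floor as they are. It adds no power to an exact test that is already stratified; the small difference runs the other way, probably from discreteness. It narrows the interval above 500 mg/g by about one point. All of this stands, and it is why the fix needs an analysis part.

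It is also fair that simple randomisation is legitimate in a declared pilot, that 20 per group can be read as a target, and that broad entry fits the referral population and the three-part response criteria. Nor does the protocol say that only a pooled rate will be reported. A SAP, not shown, may already provide by-stratum or baseline-adjusted results, and the data collected allow them under any allocation.

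Three stronger readings are tempting, and the documents support none of them:

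- A reader might infer bias. Randomisation keeps the comparison unbiased in expectation; imbalance is chance.
- A reader might infer that patients without proteinuria must dilute the effect. That holds only if the drug lowers UPC proportionally less in them, and the protocol has no evidence either way. Low power is already conceded in Limitations.
- A reader might infer that pooled planning misleads the next trial. Under the rates in step 7, the pooled figures imply 92, 49 or 25 per arm for 80% power (two-sided 5%), and the stratum above 500 mg/g implies 24. These come from assumed true rates and answer different questions: one trial with broad entry, one restricted to UPC above 500 mg/g. Neither is an error.

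**Conclusion.** The point holds as a modest design improvement. Three facts are fixed in the protocol: entry at any UPC, a relative UPC endpoint with no floor, and simple randomisation that neither secures 20 per group nor balances baseline UPC. If half the patients exceed 500 mg/g, a difference of 4 or more such patients between arms has probability 34% to 50%. Its expected effect is small, 2.5 to 4.5 points at SD 0.35, well under one standard error.

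Stratified allocation by itself brings near-equal arms, a balanced prognostic factor and up to about 10% lower SD of the crude difference. It does not remove the dependence on entry mix, which has to be handled in the analysis. The probabilities of imbalance rest on the assumed 50% share; all response rates rest on assumed UPC variability. Confidence is medium.

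**What to change.** (a) Replace simple randomisation with blocked randomisation stratified on pre-assignment UPC, >500 versus <=500 mg/g, the protocol's own threshold.

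(b) Keep the comparison of all randomised patients as primary, and stratify or adjust it for baseline UPC. Pre-specify the UPC result in the stratum above 500 mg/g as the estimate for planning a larger trial restricted to such patients. Read it always against concurrent placebo, since selection on a high baseline inflates chance falls in both arms, and report its interval. If a SAP already does this, a cross-reference is enough.

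Restricting entry, or the primary population, to UPC above 500 mg/g is a trade-off for the sponsor and not a required correction.

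Cost: a two-stratum list and a short protocol change, with no new visit, sample or patient. Study Population describes IRB submission as still under way. The UPC result must be back before assignment. The stratum may be small, about 13 to 27 of 40 at shares of one third to two thirds, and its estimate imprecise: about +/-40 points at 10 per arm, and about +/-51 at 6 per arm (0.402 versus 0.793, from median 300 and b = 0.8).

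### Current users of isosorbide mononitrate or another nitric oxide donor are not excluded, so placebo patients may be on the test drug class and active patients may receive it twice

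*Protocol*

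**What the plan says.** **Exclusions.** Under Material and Methods, the whole list is "Pregnant women and breast-feeding women. Patients >65 years will be excluded". No other section excludes, washes out or prohibits IMN or another NO donor, and none sets a lower limit for blood pressure (BP).

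**Medication history.** The Protocol and Treatment Plan says, before it describes allocation, "All current prescribed and over the counter medications will be documented". No rule then uses that list.

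**Background treatment.** Follow-up covers "Antihypertensive medications that the patients have been taking" and says that those taken "prior to enrollment will be continued". Study design names ACE inhibitors or calcium channel blockers as standard of care in both arms. It neither names nor forbids nitrates.

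**Why users may appear.** The safety section states "The FDA indication for IMN is for prevention of angina pectoris". Preliminary Studies reports a published algorithm in which NO donors are the starting antihypertensives for hypertensive patients on anti-VEGF treatment.

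**Entry routes.** The Inclusion Criteria accept patients "having new-onset proteinuria, defined as a urine protein: creatinine ratio (UPC) of >500mg/g or hypertension", or an eGFR fall of at least "25% from baseline before starting therapy". Only the hypertension route refers to BP.

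**Hypotension.** The safety section lists symptomatic hypotension as a side effect, and Criteria for Removal makes it a ground for removal.

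**The concern.** The trial estimates the effect of adding a nitrate. A patient who arrives on one is a poor test of that question in either arm. On placebo the patient still takes the drug class under test. On active the patient takes the study dose plus the existing nitrate, so the comparison is more nitrate against some nitrate.

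Two things are at stake. The first is the effect estimate: Limitations and Expected results say this pilot is to lead to a larger randomised trial, and an attenuated contrast would carry into its planning. The second is safety: doubled nitrate exposure adds to a hypotension risk that the Protocol itself recognises.

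A separate, smaller point concerns BP at entry. A patient who qualifies on proteinuria or eGFR decline may have any BP, and the Protocol does not say how this fits with what it reports about hypotension and about normotensive patients.

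**Working it through.** **1. Reading the rules as a site would.** Take a patient aged 65 or under, neither pregnant nor breast-feeding, on anti-VEGF therapy with a UPC above 500 mg/g, who already takes a nitrate.

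- Inclusion: met through UPC.
- Exclusion: none applies.
- Medication list: the nitrate is recorded, and nothing follows.
- Background treatment: if the nitrate was given for BP, Follow-up continues it. If it was given for angina, the continuation sentence does not cover it, but no rule stops it or bars entry.

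The patient is randomised, so the gap is in the text.

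**2. Size of the attenuation.** Inputs from the Protocol: 20 patients per group (Study design), and endpoints defined as change from before enrollment (Primary and Secondary End Points). The Protocol gives no share of current users, response rates, alpha or power, so the figure of 20 per group cannot be reproduced and everything below is illustration.

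Let Δ be the true contrast in non-users, f the share of current users (the same in both arms in expectation), and c the fraction of Δ that users still show, between 0 and 1. Then

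observed contrast = [(1 − f) + f·c]·Δ = [1 − f(1 − c)]·Δ.

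The loss is f(1 − c), which is at most f, reached at c = 0.

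| f | expected users in an arm of 20 | chance of at least one in the placebo arm, 1 − (1 − f)^20 | Δ = 40 points, c = 0 | Δ = 40 points, c = 0.5 |
|---|---|---|---|---|
| 5% | 1 | 64% | 38 | 39 |
| 10% | 2 | 88% | 36 | 38 |
| 20% | 4 | 99% | 32 | 36 |

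One patient is 1/20 = 5% of an arm.

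**3. What the worst case would do to power.** Assume two-sided alpha 0.05, 20 per arm and the normal approximation for two proportions:

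power = Φ{[Δ√n − 1.96·√(2p̄(1 − p̄))] / √(p₁(1 − p₁) + p₂(1 − p₂))}.

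For 20% against 60% with f = 0: Δ√n = 0.40 × 4.472 = 1.789; p̄ = 0.40, so 1.96 × √0.48 = 1.358; the denominator is √0.40 = 0.632. Then (1.789 − 1.358)/0.632 = 0.68, and Φ(0.68) = 75%.

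With c = 0 there are two versions: users respond at the active rate in both arms, or at the placebo rate in both arms. They give the ends of each range.

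| assumed rates | f = 0 | f = 10% | f = 20% |
|---|---|---|---|
| 20% vs 60% | 75% | 65–66% | 53–56% |
| 20% vs 50% | 51% | 42–44% | 34–37% |

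These are upper limits on the harm at each f. They are not estimates of it.

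**4. BP at entry: passages side by side.**

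- Inclusion Criteria: the proteinuria and eGFR routes have no BP condition.
- Safety section and Criteria for Removal: symptomatic hypotension is an expected side effect and a ground for removal.
- Preliminary Studies, on the cited algorithm: "They suggested no pharmacological treatment for normotensive patients".
- Preliminary Studies also reports that the same authors suggest NO donors for prehypertensive patients with organ damage, and pre-treatment before anti-VEGF therapy starts.

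The Protocol does not say which line of reasoning supports enrolling patients without hypertension.

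**The case against.** **Change from baseline.** Every endpoint is a change from before enrollment, so a stable nitrate is already in the baseline and does not by itself produce a placebo response. An active-arm user still receives added drug. A reader might infer that users show no contrast at all, or that the effect shrinks to exactly 1 − f. The documents do not support that; 1 − f is the worst case.

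**Randomisation.** Users fall in both arms in expectation, so the issue is attenuation, with chance imbalance possible under simple randomisation of 40 patients. It is not systematic bias of one arm against the other.

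**Users may be rare.** Standard of care is named as ACE inhibitors or calcium channel blockers, and the NO-donor algorithm is presented as one group's suggestion. This is fair: f is unknown and may be small. It limits the size of the problem but does not close the gap.

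**The algorithm does not bind the trial.** A reader might infer that enrolling normotensive patients contradicts the Protocol's own source. It does not: the algorithm is background on treating BP, while the primary endpoint is proteinuria. What remains is a request to reconcile.

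**Safeguards exist.** Weekly BP, dose reduction, removal and a monitoring board are specified. All act after randomisation, so none decides who enters. A reader might also infer that patients with low BP will probably be taken off drug. The Protocol gives no basis for that: removal requires symptoms, which it says tend to disappear with continued use.

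**Package insert.** A reader might want the insert's contraindications added to the exclusions. The Protocol does not reproduce them, so nothing here rests on them.

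**Conclusion.** The concern holds in this form: as written, the plan can randomise a patient who already takes the test drug or its class, and the Protocol's own background makes such patients plausible. That the gap exists is certain from the text. Its size is not known. The loss of contrast is between zero and f, provided that users show some part of the true effect from none to all of it. Each user is 5% of a 20-patient arm. The power figures rest further on assumed response rates and alpha. The Protocol already concedes that the trial may be underpowered, so the stronger reasons to act are a clean effect estimate for the next trial and avoiding nitrate given on top of nitrate.

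The BP point is weaker. It is an unexplained fit between sections, to be reconciled by the investigators; it is not shown to be an error in who is enrolled.

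**What to change.** Add one line to the Exclusion Criteria: current use of isosorbide mononitrate, or of any other organic nitrate or nitric oxide donor. Apply it with the medication list already recorded before assignment. It works as an entry rule only and does not ask that anyone's existing treatment be stopped in order to qualify.

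Separately, the investigators should reconcile the Inclusion Criteria (proteinuria and eGFR routes without a BP condition) with the safety section, Criteria for Removal and the algorithm described in Preliminary Studies, and state their reasoning in the Protocol. No BP value or clinical rule is suggested here.

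Cost: a short amendment and no new data. The downside is that a few patients become ineligible, which may slow recruitment slightly in a 40-patient trial.
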